Experimental research investigating the effects of cannabis on driving have been conducted with over-the-road and simulated driving tests. There has been little consistency in the methodology applied across researchers and generally a lack of replication. Investigators have studied drivers with markedly different characteristics which likely interact with the effect of the drug (e.g., patterns of substance use, prior driving experience, and age). Published studies also show a wide range of doses and delivery systems and generally fail to show an association between exposure and serum THC. Furthermore, driving simulator studies have not been conducted using anything approaching a standard set of driving challenges or tasks.

In spite of these methodological issues, there is general agreement that cannabis increases weaving. However, the relationship between cannabis exposure and magnitude of weaving remains to be determined. The impact of cannabis on lane crossings has been inconsistent. Cannabis (without concomitant alcohol consumption) generally results in slower driving speeds and greater headway distances in nighttime conditions. With respect to neurocognitive testing, cannabis has consistently been shown to impact performance under multitasking conditions.

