PURPOSE OF PRESENT STUDY: The primary purpose of the current study is to establish a standardized protocol for assessing drug impaired driving. Validation of this methodology is to be accomplished with a study using cannabis, alprazolam, and matching placebo. As part of this research effort, investigators have worked to identify the driving tasks and cognitive abilities found to be most vulnerable to the impairing effects of cannabis. In addition, an effort was made to identify the subject characteristics associated with increased vulnerability to the impairing effects of cannabis. Worked was conducted to develop a methodology for determining when drivers are safe to resume driving after drug exposure. The current study is designed to test these hypotheses.

Simulated driving will be performed using an updated version of Cognitive Research Corporation's Driving Simulator (CRCDS2 MiniSim). The prior version of this simulator has been used in dozens of driving studies submitted for regulatory review. Driving performance will be assessed using an approximate 1-hour Drug Impaired Driving Scenario (DIDS), comprised of suburban, urban and highway driving tasks. The scenarios include challenges designed to assess lane position control, speed control, safety awareness and responsivity, driving-related decision making, multitasking, and vigilance. These domains correspond to the Essential Driving Ability

Domains described by Kay and Logan (2011). In addition, cognitive functions associated with driving performance and self-report measures will also be administered.

Consistent with the principles outlined in the FDA Guidance for Industry (2017), this study includes both a positive (active) and placebo control condition. The study is designed to assess the duration of drug effects. Readiness to resume driving will be assessed using both self-report and objective testing. Subjects will include regular (daily) users and weekly users of cannabis. The intent is to assess the impact of pattern of drug use on driving performance. A cross-over study design will be utilized to maximize statistical power.

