13.5. Pharmacodynamic Analyses

All PD analyses will use the FAS Set.

The FAS will be used for the primary analysis. Summary statistics will be provided (mean, standard deviation, median, minimum, maximum) for each treatment. Figures will be provided for the within-subject difference scores by treatment and day as both a histogram and scatter plot. Data listings for driving simulator data will be provided.

SDLP data will be analyzed using a mixed model for repeated measures (MMRM) with fixed effects for sequence, period, and treatment and random effect for subject. A log-transformation of SDLP values to obtain normal distribution of data will be considered, if necessary. An unstructured covariance structure and Kenward-Roger degrees of freedom will be used. In the event an unstructured covariance structure fails to converge, a variance components covariance structure will be assumed. In addition to treatment effect, p-values for significance testing of period and sequence effects will be provided. Pair-wise comparisons of differences in means and two-sided 95% CIs on differences will be provided for all active treatments versus the placebo treatment.

The comparison of primary interest is cannabis versus placebo on Day 2 as a function of frequency of self-reported cannabis use. The statistical significance of alprazolam versus placebo ($p < 0.05$) comparison for SDLP is considered only to validate the experiment and having the ability to detect effects (i.e., assay sensitivity).

Formal statistical tests (when performed) will be 2-sided and tested at the $\alpha=0.05$ level of significance. Cannabis will be considered non-inferior to placebo if the two-sided upper 95% confidence limit on the difference in SDLP between that dose and placebo is less than 4.4 cm, and it can be concluded that the effect of cannabis on driving is less than that seen at 0.05% BAC, which is a level associated with increased crash risk. No adjustment to alpha levels will be made for either the comparison of alprazolam to placebo, or for secondary endpoints or analyses.

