As a supportive analysis, pair-wise, within-subject differences in SDLP greater than 4.4 cm in absolute value will be compared using McNemar test. Furthermore, these pair-wise, within subject differences in SDLP will be tested for symmetry about zero (Laska et al., 2012) using the maximally selected McNemar test. If there is no significant difference between placebo and cannabis and if the distribution of paired differences is symmetrical around zero, it can be concluded that cannabis does not impair driving.

Driving performance, cognitive, and self-report endpoints will be evaluated and presented using a mixed model for repeated measures. Lane exceedance will be log-transformed (more specifically $\ln[x+1]$) before analyses.

A data listing for the results will be provided. Summary tables will be presented in the same format as the primary output for:

- Driving Performance Endpoints
 - SDLP
 - Lane exceedance; including number, maximum and duration of exceedance
 - Speed related measures; including speed deviation, average speed, and excessive speed count
 - Driving safety measures; including excessive Ay (cornering speed threshold-exceeded), and total number of collisions
 - Divided attention measures; including correct responses, omission errors, commission errors, reaction time, and standard deviation of reaction time

- CogScreen SDC Test
 - Number of correct responses
 - Response accuracy
 - Standard deviation of reaction time
- CogScreen Symbol Digit Coding – Immediate Recall
 - Immediate recall accuracy
- CogScreen Symbol Digit Coding – Delayed Recall
 - Delayed recall accuracy
- CogScreen Visual Sequence Comparison Test
 - Response speed
 - Response accuracy
 - Standard deviation of reaction time
- CogScreen Divided Attention Test
 - Response speed
 - Number of premature responses
 - Response accuracy
 - Number of lapses
 - Multitasking scores
- CogScreen Matching To Sample Test
 - Response speed
 - Response accuracy
 - Standard deviation of reaction time
- CogScreen Pathfinder Number
 - Response speed
 - Response accuracy
 - Response coordination
- CogScreen Shifting Attention Test
 - Response speed
 - Response accuracy
 - Standard deviation of reaction time
- CogScreen Dual Task Test
 - Tracking errors
 - Number of boundary hits
 - Previous number response speed
 - Previous number response accuracy
 - Previous number standard deviation of reaction time
 - Multitasking scores

- Test of Variables of Attention (TOVA)

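### Both conclusion rules in section 13.5 test SDLP alone but word their conclusions as being about driving

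*Combined protocol and SAP*

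**What the plan says.** Section 13.5 contains two rules that end in a stated conclusion.

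- **Main rule.** The margin is 4.4 cm, and one variable is tested against it: "Cannabis will be considered non-inferior to placebo if the two-sided upper 95% confidence limit on the difference in SDLP" lies under that margin. When it does, "it can be concluded that the effect of cannabis on driving is less than that seen at 0.05% BAC".
- **Supportive rule.** Pair-wise "within-subject differences in SDLP greater than 4.4 cm in absolute value will be compared using McNemar test", and the same SDLP differences are tested for symmetry about zero. If cannabis and placebo do not differ significantly and the differences are symmetrical, "it can be concluded that cannabis does not impair driving".

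The protocol describes driving more broadly than SDLP. Section 5.1 says of the driving scenario: "The scenarios include challenges designed to assess lane position control, speed control, safety awareness and responsivity, driving-related decision making, multitasking, and vigilance". It links these to the Essential Driving Ability Domains, and sections 7.1 and 11.1.1 repeat the list. Section 6.2.1 presents SDLP as one key endpoint, and section 6.2.2 lists many further driving measures as other key endpoints.

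Section 13.5 also plans mixed-model analyses of the driving, cognitive and self-report endpoints. They are tabulated in the same format as the primary results, with a Wilcoxon signed rank test for collisions. No sentence gives these results a part in either rule, and none limits either conclusion to lateral control.

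**The concern.** Each rule starts from one measure of lane keeping and ends with a statement about driving. The statement is wider than the evidence that triggers it, and the protocol's own account of the scenario shows by how much.

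The rules say what may be concluded before any data are seen. Suppose cannabis increased collisions or divided-attention errors but left SDLP unchanged. The written rules would still permit the conclusion that driving is not impaired, while other tables from the same section showed the opposite. Narrowing the claim at that stage would be a post hoc change. The study is also meant to establish a standard protocol for assessing drug-impaired driving, so a conclusion rule that looks at one measure could be carried into later work.

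**Working it through.** The plan states no figure for this point, so the check is a comparison of texts, a count, and a worked pattern of results.

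**1. Input and output of each rule (section 13.5)**

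| Rule | What is tested | What is concluded | Other endpoints required |
|---|---|---|---|
| Main | Upper 95% limit for the SDLP difference, against 4.4 cm | Effect on driving below that at 0.05% BAC | None |
| Supportive | Paired SDLP differences: McNemar beyond 4.4 cm, and symmetry about zero | Driving not impaired | None |

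The condition of no significant difference in the supportive rule names no endpoint. The sentences before it in that paragraph concern SDLP only, and the other endpoints first appear in the next paragraph. The natural reading is therefore SDLP.

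**2. How many driving measures enter the rules (section 6.2)**

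- Section 6.2.1: SDLP = 1.
- Section 6.2.2: lane exceedance 3; excessive speed count 1; average speed and speed deviation 2; excessive cornering and crashes 2; divided attention 5; traffic lights, gap decisions, crash-likely events, mirrors, working memory and coherence 6. Sum: 3 + 1 + 2 + 2 + 5 + 6 = 19.
- Total: 1 + 19 = 20. The rules use 1 of the 20.

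The 13.5 table list names ten measures that are not about lane position: speed 3, cornering and collisions 2, divided attention 5 (3 + 2 + 5 = 10). The last six measures in the 6.2.2 count are not named in that list.

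**3. A pattern that exposes the gap**

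Take a trial with these results:

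- SDLP: upper limit below 4.4 cm, no significant difference, symmetrical paired differences.
- Collisions: more on cannabis than on placebo, Wilcoxon p < 0.05.
- Divided attention: more omission errors on cannabis, 95% CI excluding zero.

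The main rule is met, and so is the supportive rule. The last two lines are not inputs to either rule, so they cannot change that outcome, whatever their size. The trial may then conclude that cannabis does not impair driving while its own tables show more collisions.

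**4. Does the 4.4 cm margin widen the claim?**

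No. The margin is a quantity of SDLP. Even if it is accepted as the SDLP change at 0.05% BAC, meeting it shows that weaving rose by less than at that BAC. It does not compare cannabis with 0.05% BAC on divided attention, speed or collisions.

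**The case against.** **SDLP is the domain where an effect is most expected.** Section 5.1 reports general agreement that cannabis increases weaving, and SDLP is the weaving measure. This stands. It makes the pattern in step 3 less likely, but it does not make an SDLP result a result about driving.

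**The broad statement is only supportive and only permissive.** This stands in part. Only the supportive rule speaks of no impairment; the main rule makes the weaker comparison with 0.05% BAC. Both say what can be concluded, not what must be. The primary objective is to validate the scenario, not to clear cannabis. Even so, both sentences move from SDLP to driving.

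**The other endpoints are analysed anyway.** They are, and in the same format. But neither conclusion depends on them, and nothing says that they qualify it.

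Some stronger inferences are tempting, and the documents do not support them.

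- *The protocol predicts harm elsewhere with SDLP unaffected.* The sentence that "cannabis has consistently been shown to impact performance under multitasking conditions" is about neurocognitive testing. The sentence that cannabis "generally results in slower driving speeds and greater headway distances in nighttime conditions" is limited to night driving and calls neither change impairment. That part of section 5.1 says nothing about hazard response.
- *Slower driving hides an SDLP effect.* Nothing in the documents shows this.
- *Simulated pass rates measure the fault.* The documents give no SD for SDLP, so such rates rest on assumed values. They describe precision and the margin, not the step from SDLP to driving.

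**Conclusion.** The point holds as a mismatch between what the rules test and what they conclude. Both rules use SDLP only, and both word the conclusion as being about driving. The supportive rule goes further, because it states absence of impairment.

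The size is structural rather than numerical: 1 of 20 driving measures in section 6.2 is used, and no result on the other 19 can alter either conclusion. A better sample size or a better-supported margin would leave this unchanged.

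A reader might infer that both rules declare cannabis harmless, or that the trial is likely to do so. The text supports neither. The main rule claims less, and the protocol expects weaving to rise.

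The verdict rests on three readings:

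- The unnamed significance condition in the supportive rule refers to SDLP.
- SDLP represents lane position control. The protocol lists the domains but does not assign endpoints to them.
- No other text narrows the conclusions. Section 13 leaves detail to a separate SAP, and the combined document contains no such limit.

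**What to change.** In both concluding sentences of section 13.5, replace 'driving' with 'lane-position control (SDLP)', and use the same wording in the final SAP before database lock. Then add:

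*No conclusion about driving as a whole will be drawn from SDLP alone; the cannabis-placebo results for the other driving endpoints analysed in this section will be presented with it.*

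This changes two sentences and adds one. It needs no new data and no new analysis. The downside is a narrower claim.

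It would be better not to add a gate that permits a statement of unimpaired driving when no other endpoint shows a harmful confidence interval. Harm is not defined for average speed, since slower driving is not plainly worse. With a target of 6 to 8 completers, non-significance on a few measures is weak evidence of no harm. Seven unadjusted checks (average speed, five divided-attention measures, collisions) would also block the statement by chance in about 1 - 0.975^7 = 16% of trials, if the checks were independent and cannabis had no effect.

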13.6. Safety Analyses

Safety and tolerability of cannabis will be assessed by the incidence of TEAEs, and by changes from baseline in vital signs.

Safety data will be listed by subject and summarized by treatment. All safety summaries will be performed on the SS.

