Safety and tolerability of cannabis will be assessed by the incidence of TEAEs, and by changes from baseline in vital signs, ECG parameters, and suicidal ideation and behavior using the C-SSRS.

Safety data will be listed by subject and summarized by treatment. All safety summaries will be performed on the SS.

PK Analyses

The potential relationship between THC blood concentration and SDLP or other driving or cognition endpoints will be examined using regression techniques.

Table 1: Schedule of Assessments

Event	Screening	Double-Blind Treatment Periods 1 through 3 ^a		
		Day 1 (Admission)	Day 2	Follow-up /or ET (phone) ^b
Informed consent	X			
Inclusion/exclusion	X	X		
Demographics	X			
Medical history	X			
Epworth Sleepiness Scale	X			
Body weight/height/BMI ^c	X			
Physical examination ^d (full)	X			
Physical examination ^d (brief)		X		
HIV and hepatitis screen	X			
Urine drug & breathalyzer alcohol screen	X	X		
Vital signs ^e	X	X		
C-SSRS ^f	X			
6-lead ECG	X			
Randomization		X ^g		
Screen and Familiarize DIDS on CRCDS2-MiniSim	X (Day -14 to -3)			
Simulator Sickness Questionnaire	X (Day -14 to -3)			
Screen on CogScreen Battery and TOVA ^h	X (Day -14 to -3)			
Practice CogScreen, TOVA, and DIDS on CRCDS2-MiniSim ⁱ		X		

Administer study drug ^j			X	
Blood PK collection ^k			X	
CogScreen Subtests ^l not found., 1			X	
TOVA ¹			X	
TBD Self-Report Scales			X	
Self-perceived safety to drive question ^m Error! Reference source not found.			X	
Drug Impaired Driving Scenario ^o Reference source not found.			X	
VAS ^m			X	
Discharge ⁿ			X	
Phone call				X
Adverse events/SAEs	Ongoing from the time of consent throughout the duration of study participation			
Prior/concomitant medications ^o	X			
CRCDS2 = Cognitive Research Corporation Driving Simulator-2 nd Edition; C-SSRS = Columbia Suicide Severity Rating Scale; DIDS = Drug Impaired Driving Scenario; ECG = electrocardiogram; ET = early termination; HIV = Human immunodeficiency virus; PK = pharmacokinetic, SAE = Serious adverse event; VAS = Visual Analog Scale				

^{3a}Subjects will be admitted to NADS on Day 1 of each treatment period and then housed at the supervised off site residential facility under NADS staff supervision between the end of procedures on Day 1 and start of procedures on Day 2. Each treatment period will be separated by a washout of at least 7 days and no more than 10 days between administration of the last dose in one period and administration of the first dose in the next period.

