Cannabis will be administered once in the morning on Day 2. Effects on driving and cognition will be assessed from 30 to 45 minutes after dosing. Cognitive and self-report measures will be repeated approximately 3.5 hours post-dose to assess residual effect. There will be a one-week washout between treatment periods. Subjects will be instructed to refrain from drug use for 7 days prior to treatment period 1 and to continue to abstain from (non-study) drug use for the duration of the trial.

Alprazolam was selected as the active comparator and to further validate the CRCDs-2 and the DIDS scenario. The negative effect of Alprazolam on driving performance has been demonstrated in both on-the-road and simulated driving studies (Pearlman et al., 2019; CRC, data on file; Leufkens 2009; Leufkens & Vermeeren 2014; Mets 2011; Simen 2015; Verster 2011). Additionally, as alprazolam is the most commonly prescribed psychotropic in the U.S., use of the drug remains a concern for traffic safety.

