13.1. Data Analysis Sets

The Randomized Set is defined as all subjects who are randomized.

The Full Analysis Set (FAS) is defined as all randomized and treated subjects that have at least one primary efficacy measure (SDLP) in any treatment period.

The Safety Set (SS) is defined as all subjects administered at least one dose of any study drug.

The PK Set is defined as all subjects in the SS who have at least one collected blood sample from which a valid blood concentration can be measured.

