13.6.3. Vital Signs

Vital signs will be taken on Day 1 of each period. Vital signs data will be summarized by treatment and listed by subjects.

13.6.4. 6-Lead Electrocardiogram

Electrocardiogram will be conducted at screening. Electrocardiogram findings will be listed by subject. ECG parameters will be summarized by treatment.

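### Vital signs and ECG are to be tabulated by treatment and judged on change from baseline, but no scheduled reading follows the dose it would be tabulated under.

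*Combined protocol and SAP*

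**What the plan says.** **Criterion.** Section 13.6 states: "Safety and tolerability of cannabis will be assessed by the incidence of TEAEs, and by changes from baseline in vital signs". The synopsis is wider, judging safety also "by changes from baseline in vital signs, ECG parameters, and suicidal ideation and behavior using the C-SSRS". Section 6.2.3 lists change from baseline in vital signs, laboratory data, ECG and C-SSRS as endpoints, and section 13.3 calls for change from baseline at each time point.

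**Dosing.** Section 5.1: "Cannabis will be administered once in the morning on Day 2". The oral dose is given about 40 minutes earlier on the same day (section 7.1).

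**Vital signs.** Section 13.6.3: "Vital signs will be taken on Day 1 of each period", and then "Vital signs data will be summarized by treatment and listed by subjects". Table 1 marks Screening and Day 1, with nothing under Day 2.

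**ECG.** Section 13.6.4: "Electrocardiogram will be conducted at screening", and then "ECG parameters will be summarized by treatment". Table 1 marks Screening only.

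**Population.** Safety summaries use the Safety Set: "The Safety Set (SS) is defined as all subjects administered at least one dose of any study drug". Section 7.2 plans about 12 dosed subjects.

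**The concern.** A by-treatment safety table is read as showing what happened after each treatment. Here the readings come from before the dose. Similar columns for cannabis, alprazolam and placebo could be taken as evidence of no cardiovascular effect, when the schedule contains no measurement that could have shown one. The change-from-baseline half of the section 13.6 criterion also cannot be computed for the dose it is meant to assess.

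Three related items conflict in the same way:

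- **Laboratory data.** Change is an endpoint (synopsis and section 6.2.3), but no haematology or chemistry test is scheduled. The scheduled tests are an HIV and hepatitis screen plus urine drug, breath-alcohol and urine pregnancy tests. Section 13.4 lists the pregnancy and drug/alcohol results without summarising them.
- **C-SSRS.** Table 1 and section 13.6.6 place it at Screening. Section 8.2 item 2 implies every admission. Section 12.1.6 describes a later form covering the time since the previous visit.
- **Early termination.** The Table 1 footnote points to Day 2 safety assessments, but for Day 2 the table shows no vital signs or ECG.

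**Working it through.** The documents give no figure to reproduce, so the check places each scheduled reading against the dose.

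**1. Time points per subject.** Vital signs: Screening plus Day 1 of Periods 1, 2 and 3 = 4, of which 0 follow the same period's dose. ECG: 1, of which 0 follow any dose. If an ECG were also taken at each admission, as section 8.2 item 12 implies, there would be 4, and still 0 after that period's dose. After Period 3 there is only a phone call.

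**2. Position in time.** Appendix B puts admission at 3:00 pm on Day 1 and cannabis at 8:40 am on Day 2, which is 17 h 40 min later. No clock time is given for vital signs, so admission is used. With a 7 to 10 day washout, counted from inhaled dose to inhaled dose:
- 7 d − 17 h 40 min = 6 d 6 h 20 min after the previous dose
- 10 d − 17 h 40 min = 9 d 6 h 20 min after the previous dose

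Counting the washout to the next oral dose adds 40 minutes. About 6 to 9 days stands either way.

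**3. Contents of the vital-sign table.** Take Table 3 with 12 completers, 2 per sequence, each Day 1 reading filed under that period's treatment. Each treatment occurs once per sequence, so no subject has yet received the heading treatment when the reading is taken.

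| Column heading | Before any drug | After cannabis | After alprazolam | After placebo | Total |
|---|---|---|---|---|---|
| Cannabis | 4 | 0 | 4 | 4 | 12 |
| Alprazolam | 4 | 4 | 0 | 4 | 12 |
| Placebo | 4 | 4 | 4 | 0 | 12 |

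The three "After" columns give the immediately preceding treatment. The totals are 12 + 24 = 36 sets. The 8 readings that come next after a cannabis dose sit under the alprazolam and placebo headings.

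**4. Dropout.** If 12 are dosed and each non-completer has one or two Day 1 visits:
- 8 completers: 8 × 3 + 4 × (1 to 2) = 28 to 32 sets, of which 16 to 20 follow a different treatment
- 6 completers: 6 × 3 + 6 × (1 to 2) = 24 to 30 sets, of which 12 to 18 follow a different treatment

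A subject excluded at a third admission, after vital signs were taken, would raise either total towards 36. The count of zero does not change.

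**5. ECG table.** There are 12 Screening values. Shown under each of three treatments they make up to 12 × 3 = 36 entries.

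**6. C-SSRS, 12 completers.** Given at Screening only, 0 of 36 doses are followed by a form. Given at the Period 2 and 3 admissions with the later form, 12 × 2 = 24 of 36 are. Whether a change can be computed depends on which section holds.

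**The case against.** The strongest counter-argument concerns attribution. The plan does not define baseline for vital signs or say which Day 1 reading belongs to which treatment. Filed under the preceding treatment, 24 of 36 doses would have a later reading, so the zero depends on same-period attribution. That is correct, and the assumption should be stated. It does not rescue the tables: those readings come 6 to 9 days after dosing, none follows a Period 3 dose, and no rule in the plan files them that way.

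Other points:

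- **Safety is still observed after dosing.** TEAEs are collected throughout and summarised by treatment. Under section 12.2.1.1, a vital-sign or ECG change becomes an AE if it leads to discontinuation, needs therapeutic intervention or is judged clinically significant. This limits the consequence, but section 13.6 names vital-sign change as a separate criterion.
- **Discharge requires medical stability.** The synopsis refers to medical-monitor criteria that are not in the documents. They may include vital signs, but they schedule no recorded value.
- **A separate SAP is to follow.** It could relabel tables. It cannot supply readings that were never scheduled, and section 13.2 rules out imputation.
- **Table 1 is damaged in the text copy.** Sections 13.6.3 and 13.6.4 give the same timing in prose.
- **Appendix B shows no vital signs or ECG after dosing.** It also omits the Day 1 vital signs, so it is not a complete list and little weight is placed on it.

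**Conclusion.** The concern holds. Under same-period attribution, 0 scheduled vital-sign or ECG values follow the treatment in the column heading, and this does not depend on enrolment or dropout. As written, the by-treatment tables cannot show an effect of the treatment they name, and the change-from-baseline criterion cannot be met for the dose assessed. Of the section 13.6 criteria, only TEAEs carry information after the dose.

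The reach is limited. These are additional, descriptive endpoints with no formal test, and the SDLP analysis is untouched. This should be corrected, but it does not threaten the trial's main conclusion. The C-SSRS question stays open until its timing is settled.

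**What to change.** Reconcile the synopsis, sections 6.2.3, 13.6, 13.6.3 and 13.6.4, and Table 1 with its early-termination footnote. The documents do not show whether the schedule or the endpoint list is in error, so there are two routes.

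**If the schedule stays as it is:**
- Remove change from baseline in vital signs, ECG and laboratory data as endpoints and safety criteria.
- Replace the by-treatment vital-sign and ECG summaries with listings, or with summaries labelled as screening or admission data.
- State that the by-treatment safety conclusion rests on TEAEs.

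**If a drug effect on any of these measures is wanted:** align the schedule and the endpoint, define baseline, and state which reading belongs to which treatment. Whether and when to measure is for the sponsor and medical monitor.

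**On either route:** settle C-SSRS and ECG timing across section 8.2 items 2 and 12 (synopsis items 12 and 22), sections 12.1.6, 13.6.4 and 13.6.6, and Table 1, before deciding whether a C-SSRS change endpoint stays.

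**Cost.** The first route is a short protocol amendment, assumed to need ethics review, with no added visit, sample or assessment. The burden of changing the schedule is a separate matter and is not estimated here.
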